## B.5 Human Subjects Involvement, Characteristics, and Design

Participants will be 2000 males who are 18 years of age or older, not currently on PrEP and who have not received an HIV test in the last year. Focusing recruitment toward these individuals will allow us to examine whether the eTEST system and HBST increase testing and receipt of additional prevention services among those who rarely test and may be more difficult to reach with traditional prevention resources (i.e., clinic-based testing). Eligible participants will also report any of the following in the past 6 months: (1) anal sex (receptive or insertive) without condoms outside of a monogamous partnership with a recently tested, HIV-negative male, (2) having been diagnosed with an STI, or (3) having anal sex with an HIV-positive male. This criterion will ensure that the research is conducted among MSM who are at high risk for HIV and who meet DHHS criteria for pre-exposure prophylaxis. Since the research involves receiving HBST kits by mail, eligible participants will also be required to have a secure and stable residence to minimize the potential that tests may be stolen or diverted. This criterion was informed by past qualitative studies suggesting that most high-risk MSM prefer to receive tests by mail, as opposed to other delivery avenues (e.g., vending machine, pharmacy pickup). However, future research should address methods for providing “active” follow-up after HBSTs that are delivered via other routes, since many at highest risk may not have stable residences. Next, to be eligible, participants must currently have an Android or iOS smartphone with a data plan or a wifi internet connection at home. This ensures that the eTEST app can detect HBST kit openings when participants use the test at home. Finally, eligible participants will also be required to be fluent in either English or Spanish. All research materials will be translated into Spanish, and at least one test counselor and the LA site research assistant will be fluent in Spanish. These steps will ensure that we can explore the program’s effects specifically among Spanish-speaking Hispanic and Latino MSM. No special or vulnerable populations, as defined by 45 CFR Part 46 (e.g., prisoners, pregnant women, fetuses) are involved.

Participants will be recruited from each community (Providence, RI/Boston, MA; Los Angeles, CA; Jackson, MS) using ads placed on popular geolocation-based, gay-oriented mobile apps and sites (e.g., Grindr, Scruff, Jack’d). After clicking on the ad, interested participants will

then be taken to a mobile-optimized, interactive web application that will provide more information about the study, assess eligibility criteria, and document informed consent. Since participants will provide informed consent entirely online, we will ensure that the key study requirements are easily visible and presented in lay terms. Participants will also be required to enter their initials to indicate their consent to key parts, as well as the consent as a whole (see Section B.1. for more detail). After providing informed consent, the web app will then collect registration information from participants (e.g., name, phone number, email, address) before guiding them through a series of simple screens designed to orient them to the study.

Randomization to a study condition will take place after participants complete the study consent, and this will determine which “on boarding” (orientation) sequence participants are shown.

Participants assigned to the eTEST condition will be “funneled” toward downloading the eTEST app, while those assigned to Standard HBST and Control conditions will not be directed to the app store.

Once participants have completed this sequence, research staff will place a phone call to each participant within 24 hours to verify their contact information, ensure their understanding of the study requirements, and answer any questions about the study. Participants who do not complete this call within 72 hours of completing the orientation sequence will be considered ‘not enrolled,’ and they will be considered as withdrawn from the study. Likewise, participants who do not recall basic information about the requirements of the study (e.g., that they are expected to complete quarterly surveys online, that they will receive letters or test kits in the mail every 3 months) will similarly be considered ‘not enrolled’ and deleted from study databases. All eTest participants will be instructed to keep the app downloaded as much as possible during their time on the study. Since the SQL database associated with the app allows us to track when users uninstall it, we will contact participants who delete the app by phone and email to inquire about their interest in continuing with the study. We will also track data on app uninstalls (e.g., reasons for uninstalling and/or withdrawing) to continue examining the usability and burden of the app. eTEST participants who change their smartphones during the study period (due to an upgrade, change in service provider, or the phone being lost or stolen) will be able to re-download and login to the eTEST app from app stores appropriate to their operating system (iOS, Android). Minimal study data is stored on participants’ smartphones themselves; Instead, most data is stored on a centralized, secure database hosted on Brown University’s dedicated servers. This data is password protected and can only be accessed by essential study staff members. All participants will also be allowed to update their personal information at any time, either through the eTEST native app (for eTEST participants) or through a study web portal (for standard HBST and control participants). Quarterly surveys will also inquire about any changes in participants’ contact information (e.g., address, phone, email) each month.

As in our pilot study, to avoid influencing the study results, participants in HBST conditions (eTEST and standard HBST) will not be given explicit instructions about whether or not to use the tests sent to them (except during eTEST follow-up calls, which will encourage re-testing every 3 months). They will be informed that HBST kits will be sent to them 1 week, 3 months, 6 months, and 9 months after initially signing up, and that they can choose to take these tests or not. For eTEST participants who choose to take the tests, they will be informed that they should expect a call from an HIV test counselor within 24 hours of opening it, and that these calls are intended to provide post-test counseling, information about HIV prevention, and referrals. Push notifications on participants’ smartphones will also notify participants at the time their test kits are opened that it was detected and that they should expect a call. Participants can

refuse any part of the discussions with counselors at any time. All participants will also be informed that, should they indicate having tested positive using an HBST through the quarterly surveys, a test counselor will follow up with them within 24 hours to ensure that they have made an appointment at a local clinic for confirmatory testing and care, if needed. If not, counselors will facilitate scheduling this appointment during their calls with these participants.

For eTEST participants that open their tests, counseling calls will be placed within 24 hours. These calls will be made by paraprofessional, Bachelor's level staff members who are employees of the Brown University School of Public Health, work in a "call center" physically located at Brown University, and who have been certified as 'Qualified HIV Test Counselors' in Rhode Island. This training ensures that candidates have basic knowledge of HIV and other sexually transmitted infections, understand HIV testing and how to conduct the test, and are familiar with counseling strategies needed to address many of the issues that commonly arise in those being tested. The training is conducted each year by [name] (Co-PI). Counselors will also receive training in triaging crisis intervention, which is provided by behavioral health staff at Lifespan. Clinical assessment and analysis of mental health will remain a responsibility of the licensed study clinician.

Additional study-specific training will involve principles of conducting phone-based counseling, role plays, and direct observation through recorded counseling sessions, as well as clinic-based testing conducted at Lifespan (supervised by [name]). Drs. [name] and [name] will also provide ongoing supervision to phone counselors throughout the study. Importantly, all follow-up calls will follow the CDC's guidelines for HIV counseling, testing, and referral, and as such, will involve similar post-test counseling procedures that are currently provided by paraprofessionals and service providers in clinic- and community-based settings worldwide. Participants who test positive with HBST (those in either the standard HBST or eTEST conditions) will be assured that an initially reactive result is not a confirmed positive result. Counselors will then assist participants in scheduling an appointment for confirmatory testing with specific designated clinics at each study site (**Miriam STD/HIV Clinic** or **Fenway Health** in Boston, MA/Providence, RI; **OpenArms** in Jackson, MS; or **AHF Wellness Center** in Los Angles, CA) via three-way calling while participants are on the line. Each of these centers/clinics has standard procedures for providing newly diagnosed patients ongoing HIV care. Site PIs maintain professional affiliations with each, so that site-specific research staff can ensure/confirm whether each participant successfully made their appointments. Test counselors will conduct follow-up calls after each participant's scheduled appointments to ensure that they receive confirmatory testing. Participants with reactive test results will also be screened for suicidality during these calls, and if necessary, intervention will be provided according to National Suicide Prevention Lifeline procedures.

For each study metro area, "primary referral" sites have been designated that provide comprehensive HIV/STI prevention and care services. Each of these sites also provides HIV/STI testing services on a walk-in basis, for free. Study staff and counselors will recommend these clinics to participants first, particularly for confirmatory testing and care for any who receive reactive tests while on the study. These clinics will also serve as the primary site of referral for clinic-based tests they are to receive at the end of their study period.

Site PIs each have close connections with these clinics through their current clinical roles. Letters of Support have also been provided for each. However, each area also has several other options for HIV/STI testing, with locations that may be more convenient for some participants.

As such, a list of these clinics is provided through an HIV/STD test locator function of the app, and participants will be able to choose from these clinics, as well. Below is a list of primary sites (identified with \*) and other HIV/STI testing sites, grouped by study metro:

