## B.3 Recruitment Procedures

Ads will be placed with several MSM-oriented “hookup” apps (e.g., Grindr, Scruff, Jack’d) to recruit participants into the study. Ads will display to users who login to the apps within 30 miles of each metro. Clicking on the ad will direct users to a landing page for the eTEST study, where users can learn about the study and its requirements. A brief questionnaire will assess eligibility criteria, and those eligible will then be directed to register for the study, which will involve providing informed consent, basic personal information, and baseline questionnaire data (see Human Subjects for more details about online informed consent). The web app will then randomize participants to one of the three arms. Finally, the web app will then walk participants through downloading the eTEST app from the Google Play or iTunes stores only if they were assigned to the enhanced eTest condition. Access to the eTEST app will be restricted to users registered in the eTEST web portal who are directed specifically from that site. Participants will also be encouraged to keep the app downloaded on their phone throughout the study period and will be encouraged to register any changes in their mailing address or smartphone information (number, phone OS) as soon as possible, either through the eTEST app, web portal, or by notifying study staff.

Once users have registered, staff will conduct a brief introductory call with all participants to ensure that their information is correct and that they understand the study’s requirements. After successfully completing this call, study staff will mark these participants as ‘fully enrolled,’ activating them in the study database.

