### **Procedure**

Ads will be placed with several MSM-oriented “hookup” apps (e.g., Grindr, Scruff, Jack’d) to recruit participants into the study. Ads will display to users who login to the apps within 30 miles of each metro. Clicking on the ad will direct users to a landing page for the eTEST study, where users can learn about the study and its requirements. A brief questionnaire will assess eligibility criteria, and those eligible will then be directed to register for the study, which will involve providing informed consent, basic personal information, and baseline questionnaire data (see Human Subjects for more details about online informed consent). The web app will then randomize participants to one of the three arms. Finally, for participants assigned to the enhanced condition, the web app will walk participants through downloading the eTEST app from the Google Play or iTunes stores. Access to the eTEST app will be restricted to users registered in the eTEST web portal who are directed specifically from that site. Participants will also be encouraged to keep the app downloaded on their phone throughout the study period and will be encouraged to register any changes in their mailing address or smartphone

information (number, phone OS) as soon as possible, either through the eTEST app, web portal, or by notifying study staff.

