Once users have registered, staff will conduct a brief introductory call with all participants to ensure that their information is correct and that they understand the study's requirements. After successfully completing this call, study staff will mark these participants as 'fully enrolled,' activating them in the study database. For **control** group participants, test messages will be sent to remind users when they are due to test. Tests will include a link to a web service listing nearby clinics offering HIV testing, as well as their location, phone number, hours, and cost. For **standard** HBST group participants, staff will send an HBST kit to their confirmed shipping addresses. These participants will receive no phone-based follow-up, but can use OraSure's provided 1-800 number for questions or needs. We will follow the same steps for **eTEST** participants, except that each test kit will be fit with an Estimote™ beacon. Beacons will automatically detect when each kit is opened and relay this information to a central study database, which triggers an email notification sent to counselors. Within 24 hours of opening the kit, an HIV test counselor will call **eTEST** participants to conduct post-test counseling and refer them to other needed services, including PrEP (see Section 3C.3.6.1.). HIV test counselors will be bachelor's-level staff who are certified as HIV test counselors and will have crisis intervention training. Clinical assessment and analysis of mental health will remain a responsibility of the licensed study clinician. At least one HIV test counselor will also be fluent in Spanish. Counselors will record data during each call in the study database. In each condition, participants will receive these interventions every three months over the course of the study period: at baseline, 3, 6, and 9 months.

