## Planned Analyses

Analyses will be conducted in Year 5. To evaluate Aim 1(a), we will use factorial logistic regression to test whether rates of having completed any HIV test over the 12 month study period (assessed via self-report and/or clinic records) differ by study condition. Condition, study site (and their interaction) and other relevant covariates will be entered as predictors, allowing us to explore whether each condition's effects differ by study site. To explore the effects of study condition on regular HIV testing, we will use a generalized estimating equation (GEE) for repeated, binary outcomes, specifying whether participants tested during each 3-month study period as the focal outcome. A logit link function and independent correlation structure will be specified, with study condition, site, and relevant covariates as predictors, to test whether the odds of testing differ across time period, condition, and site. GEEs are a fitting approach for studies in which correlations between repeated measures variables are to be controlled, rather than a central focus of the analysis. For all models of **HIV testing** outcomes, a covariate reflecting whether a given participant had initiated PrEP (and when, for longitudinal models) will be added to each model, since these individuals are required to test for HIV quarterly as a part of ongoing PrEP care. Doing so will allow us to estimate the effects of study arm on HIV testing among those who did not initiate PrEP. Given that we have proposed collecting 54 more participants per site (162 total) than is required to estimate our most complex model (see Model 1b in Section 3C.3.10), we believe we will be fully powered to test this model, even with a high rate of PrEP adoption. While contamination of the control group in our pilot study was rare (only one control participant reported using a HBST), we will also track **where** each participant tested (at home, in person) in quarterly surveys. If contamination is significant, we will employ methods aimed at reducing this bias, including adding indicators of contamination as covariates or bootstrapping. To evaluate Aim 1(b), we will generate variables reflecting whether participants received testing for other STIs or risk reduction counseling during each of the four 3-month intervals of the study period. Similar GEE models will be estimated for these outcomes with time period, condition, and site as predictors, to test whether the odds of receiving each service differ across these factors. To evaluate Aim 2, we will code variables indicating whether participant reports or clinic records reflect participants having consulted with a medical provider about PrEP and/or received a PrEP prescription any time across the study period. Factorial logistic regression with study site, condition, and their interaction will be entered as predictors of this outcome, to test whether the odds of having received consultation and/or a PrEP prescription differ across each of the study sites and conditions. Overall, data from those who drop out or withdraw from the study will be used in these analyses, in intent-to-treat (ITT) fashion. Similarly, we will assume values of zero for all outcomes (i.e., non-receipt of testing or services) when quarterly assessments are missing but participants are retained in the study. Depending on the degree of missing assessments, we will use multiple imputation for these values, since data from missing assessments will likely be missing not at random.

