Research staff and study test counselors will receive notifications, both via the administrator-side of the web app and via email, that a participant has completed their “onboarding” sequence. Staff will then conduct an introductory call with each participant. This call is designed to further emphasize the key points made by during the informed consent process, verbally assess participants’ understanding of the concepts, confirm contact information, and to stress the importance of adherence to the study. These calls will last approximately 10 minutes. Based on this conversation, if staff/counselors have reason to believe that a participant is not aware of study requirements and/or may be unable to provide informed consent, he/she will notify the participant that they are ineligible. If staff/counselors believe the participant understands and can provide consent, they will be formally considered “enrolled” after all other information is checked and verified.

**Payments.** Participants will be compensated on the basis on their completion of quarterly assessments, as well as the follow-up appointment conducted at the study’s end. They will earn \$25 for the baseline survey and each of the five quarterly assessments they complete, with a \$50 bonus for completing all assigned surveys within a week of their assignment. They will also earn an additional \$50 for completing the in-person HIV test after the study is finished, for a total of \$250. Participants will be paid for each survey immediately after completing it using a reloadable debit card that will be sent to each participant after enrolling. Study payments will be managed using the shared study database and issued by staff at Brown University. We successfully used this system, as well as a similar compensation schedule, in our pilot study (see Section 3.A.5.). Compensation amounts are consistent with payments provided for research participation at Brown and other institutions, thus posing little risk of coercion.

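### Participants are randomised and shown arm-specific onboarding before the enrolment call, which then removes some of them, so the analysed set is selected after allocation

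*Combined protocol and SAP*

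**What the plan says.** **Order of steps.** B.3 describes eligibility, consent and baseline data, and then: "The web app will then randomize participants to one of the three arms". The Procedure part of B.4 repeats this and adds that "for participants assigned to the enhanced condition, the web app will walk participants through downloading the eTEST app". B.5 agrees: "Randomization to a study condition will take place after participants complete the study consent", and the allocation decides which orientation sequence is shown. The introductory call comes after that sequence in every account.

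**What the call does.** In B.4, Procedure: "After successfully completing this call, study staff will mark these participants as" fully enrolled, and only this step activates them in the study database. People who do not pass are removed on these grounds:

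- Missed call (B.5): "Participants who do not complete this call within 72 hours of completing the orientation sequence will be considered" not enrolled, and also withdrawn.
- Failed recall (B.5): people who cannot recall basic requirements are not enrolled "and deleted from study databases".
- Staff judgement (C.1.1): if staff doubt a person's awareness of the requirements or ability to consent, "he/she will notify the participant that they are ineligible".

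**Analysis.** Planned Analyses states that "data from those who drop out or withdraw from the study will be used in these analyses, in intent-to-treat (ITT) fashion". Its rule of scoring a missing assessment as zero applies only to participants still retained, and the multiple imputation it mentions is for those same values.

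**The concern.** Randomisation makes the arms comparable only if everyone randomised stays in the comparison, or if removal is unrelated to arm. Here removal happens after the participant has seen arm-specific content.

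There are plausible reasons for removal to differ by arm. Only eTEST participants are sent to an app store first. One of the two recall examples in B.5 concerns mailed letters or kits, whereas B.4 says control participants get text messages. The documents do not say whether callers know the allocation.

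If removed people are left out, bias arises when call failure depends on both arm and motivation to test. Its direction cannot be known in advance. Extra loss of poorly motivated people at the eTEST download step would inflate the eTEST rate. Extra loss among reminder-only participants would inflate the control rate.

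The call itself is legitimate: it verifies remote entrants and confirms understanding and consent. Only its position after randomisation is at issue.

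**Working it through.** **1. Can the analysis plan recover the removed people?**

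| Group | Status in B.5 or C.1.1 | Follow-up | Covered by the ITT sentence? | Outcome value |
|---|---|---|---|---|
| Fail recall | Not enrolled, deleted | None | Impossible, no record | None |
| Miss call for 72 hours | Not enrolled and withdrawn | Never activated | Possibly, as withdrawals | None stated; zero rule covers retained participants only |
| Declared ineligible on call | Ineligible | Never activated | Not stated | None stated |

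No section defines the analysis set as all randomised or asks for a count of call failures by arm. The sample-size allowance (246 raised to 300 per site) is described as being for missing data, not for exclusions between allocation and the call.

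**2. How large could the effect be?** The plan has no figure to reproduce, so this is an illustration.

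Inputs:

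- From the documents: *p* = 0.62, the pilot control rate of any testing (B.1); 2000/3 ≈ 667 per arm, taking the planned 2000 as the number randomised.
- Assumed: no true effect, so *p* is the same in both arms; share lost at the call *f*, by arm; testing rate among those lost *q*, the same in both arms.

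*If call-failers are excluded:* retained rate = (*p* − *f q*)/(1 − *f*), with *n* = 667(1 − *f*).

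Example, *f* = 20% and 10%, *q* = 0.30:

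- (0.62 − 0.20 × 0.30)/0.80 = 0.560/0.80 = 0.700
- (0.62 − 0.10 × 0.30)/0.90 = 0.590/0.90 = 0.656
- Spurious difference: 4.4 points

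The rejection probability is for a two-sided pooled two-proportion z-test at 0.05, whose correct value here is 5%. Each cell gives spurious points / rejection probability.

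| Loss by arm | *q* = 0.30 | *q* = 0.40 |
|---|---|---|
| 20% v 10% | 4.4 / 35.8% | 3.1 / 19.1% |
| 15% v 10% | 2.1 / 11.8% | 1.4 / 8.1% |
| 10% v 5% | 1.9 / 10.5% | 1.3 / 7.6% |
| 5% v 2% | 1.0 / 6.7% | 0.7 / 5.8% |
| 3% v 1% | 0.7 / 5.7% | 0.5 / 5.3% |

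With *q* = 0.50, 20% v 10% gives 1.7 points and 9.0%. With *q* = 0.62, or with equal *f* in both arms, the bias is 0 and the error 5.0%. A simulation of 40,000 trials for 20% v 10% gave 35.6% (*q* = 0.30) and 19.4% (*q* = 0.40), in agreement with the formula.

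*If call-failers are kept and scored zero:* rate = *p* − *f q*, with *n* = 667. For 20% v 10%, differences are for the arm with the larger loss:

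| *q* | Difference (points) | Rejection probability |
|---|---|---|
| 0.30 | −3.0 | 19.8% |
| 0.40 | −4.0 | 31.3% |
| 0.62 | −6.2 | 62.1% |

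Zero-scoring therefore reverses the sign, and it is worst when call failure is unrelated to testing.

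**3. Which contrast is exposed?** Take the pilot rates as those among people who pass the call. For eTEST against standard HBST (96% v 90%), zero-scoring with 10% and 5% lost gives 0.96 × 0.90 − 0.90 × 0.95 = 0.864 − 0.855 = 0.9 points, down from 6.0. The pilot gap between eTEST and control (96% − 62% = 34 points) is large compared with any bias in the first table.

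**The case against.** The strongest reply is that nothing shows the bias to be material. Loss rates are unknown, and equal, like-for-like loss does no harm. C.1.1 requires a fully correct three-question consent quiz before the baseline questionnaire, so those who reach the call have already passed a comprehension screen and the deleted group may be small. At 3% v 1% the type I error stays below 6%. This is fair, and it limits the likely size.

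Other points also stand in part:

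- The 72-hour group is classed as withdrawn, and the ITT sentence names withdrawals. Certain exclusion is therefore shown only for the deleted group. For the missed-call group the defect is a missing outcome rule and missing data.
- The ineligibility ground in C.1.1 largely overlaps with failed recall. Its distinct part, inability to consent, protects the participant.
- No section says the download step affects call completion. For standard HBST against control, the documents show no concrete driver of unequal loss beyond the different onboarding and the recall item.
- Zero-scoring is not the plan's rule for this group. It is shown only because it is an obvious default.

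One could add that people who are not enrolled were never participants. That fails: they have consented, been allocated and seen their arm's onboarding, so the label does not undo selection after randomisation.

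**Conclusion.** The concern holds. By the documents' own sequence, people are removed after allocation and after arm-specific exposure. Those who fail recall cannot be recovered, and those who miss the call have no defined outcome. This conflicts with the stated intention-to-treat analysis.

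The existence of the problem rests on the text alone; its size rests on assumption. Under the null settings above, excluding call-failers inflates type I error from 5% to about 6–7% for losses of 5% v 2%, and to 19–36% for 20% v 10%, when call-failers test at 30–40%. The sign follows whichever arm loses more. There is no bias if the loss is the same in size and kind across arms, or if call-failers test at the same rate as everyone else. The large eTEST-against-control gap seen in the pilot would probably survive; the closer contrast with standard HBST might not.

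It should be settled before recruitment, because deletion is irreversible and could remove even the count of people lost by arm.

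**What to change.** **Preferred.** Have the web app randomise only when staff mark the participant fully enrolled after the introductory call, and then release the arm-specific onboarding and the app link. Make the call script and recall questions the same for all arms. Call failures then become pre-randomisation screen failures, and the call keeps its verification and consent purposes.

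*Cost.* One trigger moves in the web app, and B.3, B.4 (Procedure), B.5 and the onboarding order in C.1.1 are amended. eTEST participants get the app link after the call instead of in the first session, so some may not download it. That matters because kit-opening detection needs the app, but it becomes non-adherence inside the ITT set and not an exclusion. Download rates should be monitored.

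**If allocation must stay before the call.**

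- Delete no randomised record. For anyone whose data cannot be kept, retain at least a de-identified entry with arm and reason.
- Define the ITT set as all randomised, and report call failures by arm and reason.
- State the outcome rule for people never activated, and add a sensitivity analysis that varies their assumed testing rate by arm.
- Reconcile when baseline data are collected: B.3 puts this before randomisation, B.4 (Measures) after enrolling. Only the former allows call failures to be compared with others at baseline.

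This fallback makes the problem visible but does not remove it, since any outcome assigned to these people is an assumption.
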